5.2 Treatment Administration

Subgam-VF should only be infused subcutaneously using an infusion pump. Subgam-VF can be infused into the following sites: abdomen, thigh, upper arm and/or lateral hip.

The dose of Subgam-VF can be given into multiple infusion sites (although this should be no more than six sites, and eight sites for subjects ≥100 kg). If more sites are needed to achieve a full dose, then the sites can be used consecutively, but the infusions should be at least two inches apart.

Only one batch of Subgam-VF should be infused during any one infusion session.

Subgam-VF infusions will be administered in accordance with the table below, the maximum volumes and flow rates may be reduced according to tolerability.

Table 3 - Recommended infusion flow rates for Subgam-VF

	Volume	Rate
First infusion	20 mL/site	20 mL/hr/site
Maximum at subsequent infusions	Up to 30 mL/site	Up to 30 mL/hr/site

- Up to six infusion sites can be used simultaneously. Subjects weighing ≥100 kg may use up to eight sites if necessary. If more sites are required, these must be used consecutively (during the same infusion).
- Any increase in flow rate or number of sites should first be tried whilst the subject is in the clinic
- For young children or adults of below average weight lower flow rates may be used, depending on tolerability.

Details on how to prepare and administer the Subgam-VF infusion can be found in the Pharmacy Manual.

Full training must be provided to the subject prior to self-administration at home or other appropriate setting. It is aimed to start home-therapy at Week 3, however if the subject requires further training this will be provided (i.e. it is not mandatory that the infusions are performed at home from Week 3).

Lack of tolerance at any given rate must be recorded as an AE at that rate. If a subject has had the same treatment related AE at the same rate twice, and those AEs have been recorded, then subsequent infusion rate should be halted at the previously highest tolerated rate.

If any AE(s) occur, these will be documented as detailed in section 10.3 of the protocol. The infusion may then be resumed at a rate tolerated by the subject.

5.3 Randomization and Blinding

This is an open-label, non-randomized study.

5.4 Plasma Concentration Measurements

All subjects will undergo a PK assessment (see Table 1 and 2 for the sampling time points).

Where possible, samples from Steady State Day 1 (24 hours after the infusion at Week 21 or if delayed, up to Week 25) onwards may be collected at the subject's home by an appropriately qualified member of the study team. Alternatively a Home Health Agency may be utilized to take the PK samples outside of the investigational site. The subject would be required to sign an IRB/EC approved consent form to permit the site to share the subject's details with the agency in order for them to collect the sample.

The timing of the collection of blood samples for PK should be as per Table 1. The scheduling has been selected to ensure achievement of steady state of Subgam-VF.

A variation of <10% is allowed in the timing for samples as follows:

Steady State Day 1 (24 hours) ± 2 hours,

Steady State Day 2 (48 hours) ± 4 hours

Steady State Day 3 (72 hours) ± 6 hours

Steady State Day 5 (120 hours) ± 8 hours

Steady State Day 7 (168 hours) ± 12 hours.

All PK parameters will be calculated based on absolute (uncorrected) and baseline-adjusted (i.e. trough-adjusted at steady state) concentrations.

Details of the PK methods will be outlined in a PK Analysis Plan. The PK Analysis Plan will be finalized before database lock.

6. STUDY ENDPOINTS

6.1 Primary Efficacy Endpoint

As this is a pharmacokinetic and safety study, no formal efficacy analyses are planned.

6.2 Safety Endpoints

Safety endpoints include assessment of adverse events and adverse drug reactions, significant changes in vital signs, safety laboratory parameters (including kidney and liver function and Direct Coombs' test), virology, physical examination or medical history during the study.

The variables used to assess safety will be the following:

- Adverse Events
 - The number and percent of adverse events (AEs) including infusion site reactions.
 - The number and percent of infusions associated with one or more AEs that begin during the infusion, up to one hour, 24 hours, 48 hours or within 72 hours after completion of the infusion.
 - Adverse reactions, defined as any AE occurring during the infusions or within 72 hours of the infusion completion OR any AE classed as product related.
 - Thrombotic events
 - Nature, severity, and frequency of AEs (tolerability)
 - Suspected unexpected serious adverse reactions (SUSARs), if any
- Vital signs
- Clinical laboratory tests including tests for hemolysis
- Transmission of viruses
- Physical examination

6.3 Pharmacokinetic Endpoints

In addition to the PK variables determined as described in the PK plan, the following PK parameters will be determined:

- Trough serum IgG levels (measured before every infusion administered at the study site).
- Trough levels of serum IgG subclasses will be measured prior to certain infusions.
- Levels of specific antibodies (*Haemophilus influenzae* B, *Streptococcus pneumoniae*, *Measles*) will be measured prior to certain infusions.

7. INTERIM ANALYSIS

There is no planned interim analysis for this study, however after sufficient adult PK data has been collected, a review of the blood sampling schedules for children will be performed and the PK sampling will be optimized and reduced if possible.

8. SAMPLE SIZE AND STATISTICAL POWER CONSIDERATION

This study will enroll up to 50 subjects to ensure 30 evaluable subjects. A sample size of approximately 18 adults (aged 16-75 years) and 12 children (aged between or equal to 2 and 15 years), has been decided as recommended by the FDA guidance for IGIV products¹. For this study, the children will be enrolled across the age groups of 2 to 5 years, 6 to 11 years, and 12 to 15 years with a minimum of four in each age group. Data will be compared to historical data from previous Gammaplex IGIV studies. All the subjects will undergo a PK assessment.

Assuming no true difference exists in average exposure compared with the historical data, 30 evaluable subjects will give greater than 98% power of concluding equivalence assuming a between-subject coefficient of variation (CV) of 18.2 % (equivalently, a standard deviation of logged data of 0.181). If there is a true difference of 10%, power drops to 86%.

9. ANALYSIS POPULATIONS

9.1 Intent-to-treat (ITT) Population

All subjects who receive at least one infusion of Subgam-VF will be included in the intent-to-treat (ITT) population. The ITT population will be used for all safety analyses and summaries of demography.

10. GENERAL ISSUES FOR STATISTICAL ANALYSES

Subject listings of all data represented in the electronic CRF (eCRF) will be provided. Measurements from subjects excluded from the predefined analysis populations or extra measurements (such as unscheduled or repeat assessments) will not be included in summary tables unless specified otherwise, but will be included in the subject listings. In general, the subject listings will be sorted by subject number and assessment date (and time) if applicable.

Unless otherwise specified, descriptive statistics will include the number of subjects with data to be summarized (n), mean, standard deviation (SD), median, minimum and maximum. The same number of decimal places as in the raw data will be presented when reporting minimum and maximum, 1 more decimal place than in the raw data will be presented when reporting mean and median, and 2 more decimal places than in the raw data will be presented when reporting SD.

All categorical/qualitative data will be presented using absolute counts and percentages. The total number of subjects in the treatment group overall (N) will be used as the denominator for percentage calculations, unless stated otherwise in the table shell. All percentages will be presented as one-decimal point, unless otherwise specified. Percentages equal to 100 will be presented as 100% and percentages will not be presented for zero frequencies.

All analyses and summaries will be produced using SAS® version 9.2 (or higher).

10.1 Baseline Value

Unless otherwise specified, baseline is the last available observation before the start of the first infusion of study drug.

10.2 Methods for Withdrawals and Missing Data

Data from subjects who withdraw will be included, where possible, in all summaries and analyses. All summaries and analyses will be based on observed data. No imputation will be done for missing data.

10.3 Adverse Events

AEs will be documented from the date the informed consent form is signed until 28 days after the last dose of Subgam-VF is infused. All AEs will be coded by using MedDRA, Version 18.0.

Although all AEs will be listed, summary tables will be based on treatment emergent adverse events (TEAE), defined as those with onset date between first infusion date and 28 days after the last infusion.

10.4 Concomitant Medication

Concomitant medications will be coded by using the World Health Organization-Drug Dictionary (WHO-DD) Version March 1, 2015. Concomitant medications are defined as all medications (excluding study drug) taken while "on study". The on-study period is from the date of the first infusion of Subgam-VF up to and including the date of the last visit (the telephone follow-up at week 30).

If the start date of a concomitant medication is missing, then the start date will be estimated using the first infusion date. If the imputed start date is after the stop date, the start date will be set to the day prior to the stop date. If the stop date of a concomitant medication is missing, then the medication will be treated as ongoing.

Other non-complete dates will use the same algorithm as above for TEAE.

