# 7.16. Routine Pre-medications

Routine premedication to reduce potential adverse effects associated with the SCIG infusion are discouraged. Exceptions:

- Premedication will be permitted if a subject has reported systemic adverse events on two Subgam-VF infusions.
- If required, local anesthesia (for example Emla cream) is also allowed before any infusion to reduce the pain associated with needle insertion.

The routine long-term use of corticosteroids is not allowed. Oral and parenteral steroids are allowed if the average daily dose is < 0.15 mg prednisone equivalent/kg/day. Short or intermittent courses of > 0.15 mg/kg/day are allowed if required.

If a subject who previously required premedication before infusion with a licensed or experimental (Phase III or IIIb) IgG product is enrolled, their previous use of premedication, as well as associated side-effects must be recorded on the eCRF.

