5. STUDY METHODS

5.1 Overall Study Design

This will be a Phase III, multicenter, open-label, non-randomized study. Up to 50 subjects will be enrolled to ensure 30 evaluable subjects. At least 18 subjects will be adults* (aged 16-75 years) and 12 will be children split between the age groups 2 to 5 years (i.e. not reached their 6th birthday), 6 to 11 years (i.e. not reached their 12th birthday) and 12 to 15 years (i.e. not reached their 16th birthday).

*The definition of an adult as ≥ 16 years is as per the FDA guidance for PK studies. Note this does not affect the requirements for consent/assent, for which each site should follow their IRB guidelines.

Subjects will receive 26 infusions (weeks) of Subgam-VF at a weekly dose equivalent to 1.37 of their IGIV dose (expressed as mg/kg/week). If the subject was already receiving a weekly SCIG IgG there will be no dose adjustment. Pharmacokinetics and safety of Subgam-VF will be assessed.

The schedule of assessments is given in Table 1.

All subjects will undergo a pharmacokinetic (PK) profile after the 21st infusion of Subgam-VF. Pharmacokinetic Assessment Schedule for Subgam-VF (Week 21 to Week 22) is given as outlined in Table 2.

Table 1 Schedule of Assessments

Assessment																		
(Wk)	Screen	1 ^a	2	3 to 4	5	6 to 8	9	10 to 12	13	14 to 16	17	18 to 20	21	22	23 to 25	26	27 FU ^b	30 Telephone FU°
Clinic Visit No.	1	2	3		4		5		6		7		8	9		10	11	
Informed Consent	Х																	
Inclusion /Exclusion Criteria / Eligibility	Х	Х																
Medical History	Х																	
Physical Examination	X	Х							Х								Χ	
Weight	X	Х	Х		Х		Х		Х		Х		Х	Х		Х	Χ	
Chest X-ray – if not available in previous 12 months		Х																
Vital signs ^d	Х	Х	Х		Х		Х		Х		Χ		Χ	Х		Х	Χ	
Infusion with Subgam-VF		Х	Х	Х	Х	Х	Х	Х	Х	Х	Х	Х	Х	Х	Х	Х		
Infusion Site Inspection for reactions		Х	Х	Х	Х	Х	Х	Х	Х	Х	Х	Х	Х	Х	Х	Х		
Concomitant medications	Х	Х	Х	Х	Х	Х	Х	Х	Х	Х	Х	Х	Х	Х	Х	Х	Х	Х
Adverse event reportinge	Х	Х	Х	Х	Х	Х	Х	Х	Х	Х	Х	Х	Х	Х	Х	Х	Х	Х
TEE examination ^f	X																Χ	
Hematology	X	Х	Χ		Χ		Χ				Χ						Χ	
Biochemistry	X	Х	Х		Χ		Χ				Χ						Χ	
Urinalysis	Χ	Х									Χ						Χ	
HCG urine pregnancy test	X																	
lgG trough levels	X	Х	Х		Χ		Х		Χ		Χ		Χ	Х		Х	Х	
IgA, IgM ^g	Х																	
lgG subclasses	X																Χ	
Specific anti-bodies h	X																Χ	
Virology i	X																Х	
Parvovirus B19 ^j		Х	Х														Х	
Direct Coombs' Test k		Х	Χ						Χ								Х	

Assessment																		

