11.5 Prior and Concomitant Medications

Prior and concomitant medications will be coded using WHO-DD (Version March 1, 2015). Prior medications are defined as those with a start date before the date of the first Subgam-VF infusion.

The number and percent of subjects taking prior and concomitant medications will be summarized by classification according to preferred term and route. If a subject has taken a prior/concomitant medication more than once, the subject will be counted only once in the respective total.

The number and percent of subjects taking pre-medications during the study will also be summarized by preferred term. These will be identified by a review of the coded medications.

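### A medicine recorded at Screening with no start date, and still taken at the first infusion, is wrongly left out of the prior-medication summary

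*SAP*

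**What the plan says.** SAP 10.4 deals with incomplete medication dates:

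- Missing start: "If the start date of a concomitant medication is missing, then the start date will be estimated using the first infusion date".
- Override: "If the imputed start date is after the stop date, the start date will be set to the day prior to the stop date".
- Missing stop: "If the stop date of a concomitant medication is missing, then the medication will be treated as ongoing".
- Other incomplete dates are sent to an algorithm said to have been given above for treatment-emergent events.

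The same section makes a medicine concomitant if it was taken between the first infusion and the Week 30 telephone call. That definition looks at use and does not need a start date.

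SAP 11.5 supplies the other class: "Prior medications are defined as those with a start date before the date of the first Subgam-VF infusion". It then summarises subjects by preferred term and route, counting each subject once per medicine.

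In SAP 5.1, Table 1 (and Protocol Appendix IV, Table 2), the "Concomitant medications" row is marked at Screening and at every later column. Protocol 7.1 places the first infusion 7 days after Screening, give or take 1 day.

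SAP 10.2 says that missing data will not be imputed.

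**The concern.** A medicine written down at Screening was in use before treatment began, whatever its start date. The SAP has no rule that uses the visit at which a medicine was recorded. It replaces the missing date with the one date that just fails the test for a prior medicine, so the imputation overrides what the trial already knows.

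The case is foreseeable. Protocol 7.6 expects chronic conditions that need treatment during the study and asks for that treatment to be recorded at Screening. Start dates of long-standing medicines are plausibly among the harder ones to recover, though the documents give no figures on this.

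At stake is the accuracy of the table describing what subjects were taking before Subgam-VF. No inferential result is involved.

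**Working it through.** The plan gives no figure to reproduce. The check applies the written rules to test records.

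**Inputs**
- Day 0 is the first infusion. Screening falls on day −8 to day −6 (7 ± 1 days earlier, Protocol 7.1).
- Start missing (SAP 10.4): set start = 0; if 0 > stop, set start = stop − 1.
- Stop missing (SAP 10.4): ongoing.
- Prior (SAP 11.5): start < 0.
- Concomitant (SAP 10.4): still taken on or after day 0, so stop ≥ 0 or ongoing.

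**Test records**, all with the start date wholly missing. The true starts (day −300 and day +40) are illustrative.

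| True start | Stop | Imputed start | Prior under SAP | Truly prior | Concomitant under SAP | Truly concomitant |
|---|---|---|---|---|---|---|
| −300 | missing | 0 | no | yes | yes | yes |
| −300 | +30 | 0 | no | yes | yes | yes |
| −300 | 0 | 0 | no | yes | yes | yes |
| −300 | −1 | −1 − 1 = −2 | yes | yes | no | no |
| −300 | −3 | −3 − 1 = −4 | yes | yes | no | no |
| +40 | missing | 0 | no | no | yes | yes |
| +40 | +50 | 0 | no | no | yes | yes |

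The first three rows are wrong on prior status. Each is a medicine begun before day 0 and still taken on or after it. In the third row the override does not act, because 0 is not after 0. The next two rows are rescued by the override. The last two, begun during treatment, are correctly not prior. Concomitant status is right in all seven.

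**Does the imputed date feed the prior definition?** The SAP does not say so outright, but two points support it. Concomitant status does not depend on a start date, so prior status is the only medication class that needs one. And an imputed start of day 0 can be later than the stop date only if the medicine ended before day 0, so the override is written for medicines that were not taken on study. Its visible effect is to keep them prior.

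**Related gaps in the same rule.** SAP 10.2 excludes imputation and 10.4 imputes. If 10.2 were followed instead, a missing start date would leave prior status undecided, and the Screening record would still go unused. For partial dates, 10.3 gives the collection period, the coding dictionary and the definition of a treatment-emergent event, but no date algorithm. The result for a medicine with, say, only a known year cannot be worked out from the SAP.

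**The case against.** The strongest case on the other side is that little depends on this, and that much of the exposure may not arise.

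- The rule applies only to wholly missing dates. Long-standing medicines may have a known year and fall under the separate partial-date sentence. This stands as a limit on the number of records, although that sentence points to an algorithm that is not there.
- The table counts subjects once per medicine, so another dated record of the same medicine can keep a subject in the prior count. This also stands.
- The eCRF may carry a flag for medicines begun before the study. The documents do not show one, and no SAP rule uses one.
- The primary PK comparison and the 40% infusion adverse-event criterion do not use prior-medication data. This stands in full.

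A reader might go further and infer that a long-standing analgesic with an imputed start on day 0 would be counted as premedication, although systemic premedication is restricted: "Premedication will be permitted if a subject has reported systemic adverse events on two Subgam-VF infusions". The documents do not support that chain. SAP 11.5 says of premedications: "These will be identified by a review of the coded medications". It sets no start-date criterion and does not limit the review to drug names, so the imputed date neither creates nor cures any doubt about premedication. Protocol 7.16 also allows local anesthesia before any infusion.

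Nor can it be said that such medicines will be reported as begun with Subgam-VF. The 11.5 tables are by preferred term and route, and nothing states that imputed dates are displayed.

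**Conclusion.** The point holds in a narrow form and is minor. As written, SAP 10.4 and 11.5 remove prior status from a medicine that meets three conditions: it is known to have been in use before the first infusion, its start date is wholly missing, and it is still taken on or after the first infusion. Where all three hold, the result is wrong every time.

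It would be too strong to say that every ongoing medicine without a start date is misclassified, because one begun during treatment is correctly not prior. It would also be wrong to turn a share of undated ongoing medicines into the same share missing from the prior table. That table also holds medicines stopped earlier, which are unaffected, and it counts subjects rather than records. The documents give no rate of missing start dates, so no size can be put on the shortfall.

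The conclusion assumes that the imputed date is the one used in 11.5 and that no unstated eCRF flag overrides it. The consequence is limited to one descriptive summary.

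**What to change.** - **SAP 10.4, one added sentence:** when the start date is wholly missing, a medicine recorded at Screening, or otherwise documented as in use before the first infusion, is classed as prior, and also as concomitant if still taken on or after the first infusion; the imputed first-infusion date does not override this.
- **SAP 10.2 and 10.4:** state that the date rules in 10.4 are an exception to the ban on imputation, or remove the conflict in another way.
- **SAP 10.3 or 10.4:** write out the partial-date algorithm that 10.4 refers to.

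The cost is a short SAP amendment and minor programming. The reclassification uses the Screening medication record that the schedule already requires, so no new data are needed. It is best done before database lock.

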10.5 Multicenter Considerations

Centers will not be pooled for analysis.

10.6 Multiple Comparisons and Multiplicity

No adjustments will be made for multiple comparisons.

10.7 Data Safety Monitoring Board (DSMB)

No DSMB is planned for this study.

10.8 Presentation by Age Group

All tables will present data for all adults, pediatrics, and all subjects. Selected tables, as identified in the relevant section, will be repeated for the pediatric age subgroups, in the following order:

- All subjects
- Adult subjects
- Pediatric subjects
- Pediatric subjects aged 2-5 years
- Pediatric subjects aged 6-11 years
- Pediatric subjects aged 12-15 years

11. SUBJECT DISPOSITION

The number of subjects enrolled, completing the study, and discontinuing the study will be presented in a summary table and a listing, along with the reason for discontinuation. The table will be based on the all subjects.

11.1 Protocol Deviations

All protocol deviations will be listed by subject for the ITT population.

11.2 Demographics and Baseline Characteristics

Demographic and baseline characteristics will be presented in a summary table and a listing. The summary table will be based on the Intent-to-Treat population. Demographic variables will be age, gender, race and ethnicity. Baseline and disease characteristics are height, weight, BMI, the results of a chest x-ray, diagnosis and prior infections in the 6 months prior to screening. The following data will be listed only: prior IgA and IgM levels in the 12 months prior to screening or at screening, and results of pregnancy testing at screening.

Age will be summarized as both a continuous variable and using the categories:

- 2-5 years
- 6-11 years
- 12-15 years
- ≥ 16 years.

Age (years) will be calculated as (date of informed consent – date of birth)/365.25, rounded down to the nearest whole number.

11.3 Medical History and Chronic Conditions

Descriptions of medical history findings and chronic conditions will be coded using the Medical Dictionary for Regulatory Activities (MedDRA), Version 18.0. Medical history and chronic conditions will be summarized by the number and percent of subjects within each body system and preferred term. These summaries will be based on the Intent-to-Treat population.

